1 ABSTRACT

1.1 Type of study

A pilot, prospective, single blind, no controlled study with ultrasound evaluation of skin in patients undergoing treatment with a multidisciplinary program that includes diet, physical exercise and cosmetic cream.

1.8 Study design

Prospective, no controlled pilot study on the structural changes in subcutaneous tissue observed by skin ultrasound, in patients with edematous fibrosclerotic panniculopathy (cellulite) after a multidisciplinary treatment program including diet, physical exercise and cosmetic cream.

1.9 Primary objective

To evaluate the structural changes (trabecular texture) in subcutaneous tissue detected by skin ultrasound in patients with cellulite after a multidisciplinary treatment that includes diet, physical exercise and cosmetic cream.

1.10 Secondary objectives

- To evaluate changes in skin thickness assessed by skin ultrasound after multidisciplinary treatment.
- To evaluate the changes in cellulite severity in the involved areas after the multidisciplinary treatment from photographic images.

1.11 Disease in study

Non-infectious skin cellulite or edematous fibrosclerotic panniculopathy

1.12 Therapy in study

Multidisciplinary program including diet, physical exercise and cosmetic cream (PnKCelulitis® program)

1.13 Primary Outcome Measure

Differences in trabecular structure of subcutaneous tissue between prior to starting multidisciplinary treatment and after the end of this treatment, assessed by skin ultrasound.

1.14 Study population and number of subjects

Women with non-infectious skin cellulite (edematous fibrosclerotic panniculopathy), submitted to the PnKCelulitis® multidisciplinary treatment program including diet, physical exercise and cosmetic cream.

The number of patients expected to be included is 30.

1.15 Follow-up and duration of the study

Patient follow-up will be 10 ± 1 weeks to 18 ± 1 weeks, depending of treatment duration because of the degree of cellulite.

3 GENERAL INFORMATION

Study title	Pilot study for ultrasound evaluation of structural changes in subcutaneous tissue in patients with cellulite after a multidisciplinary anti-cellulite treatment (PnKcelulitis® program). PROCESS study
Protocol Code:	PNK-CEL-2016-06
Type of study	A pilot, prospective, single blind, no controlled study with ultrasound evaluation of skin in patients undergoing treatment with a multidisciplinary program that includes diet, physical exercise and cosmetic cream.
Therapy in study	Multidisciplinary program including diet, protein supplements, physical exercise and cosmetic cream (PnKcelulitis® program)
Sponsor's details	PNKDIET, S.L.U. [name] [contact].
Principal investigator:	[name] Department of Dermatology. Hospital de la Santa Creu i Sant Pau
Research collaboration	[name] [name] Department of Dermatology. Hospital de la Santa Creu i Sant Pau
Primary objective	To evaluate the structural changes (trabecular texture) of subcutaneous tissue detected by skin ultrasound in patients with cellulite after a multidisciplinary treatment that includes diet, physical exercise and cosmetic cream.
Study population	Women with non-infectious skin cellulite (edematous fibrosclerotic panniculopathy), submitted to the PnKcelulitis® multidisciplinary program including diet, physical exercise and cosmetic cream.
No. of subjects	A pilot study is expected to include 30 patients
Follow-up	Patient follow-up will be 10 ± 1 weeks to 18 ± 1 weeks, depending on the degree of cellulite. With two controls: initial and final

4 INTRODUCTION AND RATIONALE OF THE STUDY

Cellulite is a skin disorder that modifies the subcutaneous adipose tissue causing changes in the body shape and skin. It is accompanied by changes in the microcirculation of the connective tissue, causing morphological, histochemical and biochemical modifications to the tissue. It is characterized by the padded and nodular appearance of the skin in sloping areas.

Also known as 'deforming skin panniculitis', 'nodular lipodermatosclerosis', 'gynecological lipodystrophy' or 'edematous fibrosclerosis', among others, it is a disorder that affects 85-98% of women after puberty and is considered a women's secondary sexual feature^{1,2}.

With a multifactorial etiology, its physiopathology is complex and includes: expansion of the subcutaneous fat, formation of fibrotic septa in the dermis, dermal laxity and atrophy³.

In addition to the direct effect of hormonal changes; genetic factors ,a family tendency to abnormal fat deposition and poorly developed muscle mass are some of the factors influencing the development of cellulite. Bad eating habits are other non-hormonal risk factors for the development of cellulite. Increased intake of carbohydrates and fats increases hyperinsulinemia which, among other effects, intensifies the lipogenesis process. Also, a poorly balanced diet with a lot of preservatives and salt in food increases fluid retention and edema.⁴.

Some additional factors are poor physical exercise and a sedentary lifestyle that disrupt the proper functioning of microcirculation and support the accumulation of adipose tissue⁴.

A wide range of therapies have been suggested for the treatment of cellulite, from weight loss (the most frequent), to treatments of skin massage and the use of topical agents and oral supplements. Massages reduce edema and there is also some evidence of increased collagen synthesis after such treatments. Likewise, their benefits might be explained by their likely effects on fibroblast activity stimulation and decreased adipocyte activity. Generally, topical creams contain different agents but have been poorly studied. Xanthines, botanical extracts, fragrances, and retinoid and PPAR receptors ligands seem to provide some results, through the reduction of adipogenesis and an increased thermogenesis that would improve microcirculation and the collagen synthesis. In addition, many oral agents for weight control (hydroxycitrate, epigallocatechin gallate, conjugated linoleic acid, etc.) are being researched and some of these agents, such as conjugated linoleic acid (CLA), seem to improve the signs of cellulite. Regular exercise and a proper diet can help control weight and therefore the appearance of cellulite.²

The PnKCelulitis® Program is a new treatment aimed at improving the signs of cellulite by combining different types of therapies. Its multidisciplinary approach includes: diet, physical exercise and the topical application of a cream. The dietary regimen includes a hypocaloric diet and protein supplements. The diet, which in the first few weeks is also ketogenic with a very restricted supply of carbohydrates, is able to increase lipolysis and reduce adipose tissue also improving fluid drainage. The supply of protein

supplements along with physical exercise seeks to increase muscle mass and reverse the underlying flaccidity, while improving microcirculation and mobilizing fat deposits. The treatment is complemented by the application of a cosmetic cream whose components contribute to reduce lipogenesis and improve circulation.⁵.

This study is aimed at evaluating the degree of benefit obtained through this new multidisciplinary anti-cellulite treatment, semi-objectively, from the changes observed in the dermis structure and the subcutaneous tissue by means of skin ultrasound⁶, as well as the visual changes on skin appearance in the areas involved.

5 STUDY OBJECTIVES

5.1 Primary objective

To evaluate the structural changes (trabecular texture) in subcutaneous tissue detected by skin ultrasound in patients with cellulite after a multidisciplinary treatment that includes diet, physical exercise and cosmetic cream.

5.2 Secondary objectives

- To evaluate changes in skin thickness assessed by skin ultrasound after multidisciplinary treatment.
- To evaluate the changes in cellulite severity in the involved areas after the multidisciplinary treatment from photographic images.

6 STUDY DESIGN

6.1 Type of study

A pilot, prospective, single blind, no controlled study with ultrasound evaluation of skin in patients undergoing treatment with a multidisciplinary program that includes diet, physical exercise and cosmetic cream. .

6.2 Randomization process

Not applicable

6.3 Type of control

Not applicable.

6.4 Masking Techniques

Both the ultrasound images and the photographic images will be blindly assessed by two independent researchers, who will not know the identity of the patients evaluated.

7 SUBJECT SELECTION

7.1 Study population

Women with non-infectious skin cellulite (edematous fibrosclerotic panniculopathy), submitted to the PnKCelulitis® multidisciplinary treatment program including diet, physical exercise and cosmetic cream.

7.2 Inclusion criteria

- Women aged over 18
- Women who, regardless of their inclusion in this study, will undergo the anti-cellulite multidisciplinary treatment program (PnKCelulitis® program)
- Women who agree to participate and sign the Informed Consent

7.3 Exclusion criteria

- Pregnant or lactating women.
- Women in whom the ketogenic diet is contraindicated and therefore they cannot be on the multidisciplinary program's diet. These contraindications include:
 - Eating disorders, alcoholism, and/or drug addiction.
 - Severe psychological disorders (eg schizophrenia, bipolar disorder, depression ...).
 - Treatment with dicumarinic anticoagulants (Sintrom®) or cortisone.
 - Liver failure.
 - Severe kidney failure (gfr <30).
 - Type 1, and type 2 Diabetes mellitus if insulin dependent.
 - Hemopathies.
 - Cancer.
 - Cardiovascular or cerebrovascular diseases.
 - Acute attack of gout.
 - Nephrolithiasis verified by ultrasound.
 - Cholelithiasis verified by ultrasound.
 - Electrolyte imbalance, according to medical criteria.
 - Orthostatic hypotension.

7.4 Number of subjects

The number of subjects expected for this pilot study is 30 women.

7.5 Rationale of sample size

In an exploratory pilot study to test a concept, it has been estimated that 30 patients will be sufficient to analyze results.

Being a pilot study, it is understood that the estimation of the sample size is not necessary.

7.6 Recruitment period

We expect a 1-month recruitment period

7.7 Criteria for withdrawal or dropouts

Dropouts are those women who do not comply with the treatment schedule or do not complete treatment time established in the protocol of the multidisciplinary program.

8 TREATMENT DESCRIPTION

Multidisciplinary program for the treatment of cellulite

The PnKCelulitis® Program consists of a multidisciplinary program that includes diet, protein supplements, physical exercise and anti-cellulite cream. Its duration depends on the degree of cellulite and is structured in 3 parts called "processes" (restructuring process, drainage process and toning process). Each of them consists of:

- Dietary regimen. The dietary regimen during the first part of the program (restructuring process 1 and 2) consists of a ketogenic low calorie diet (800-1200 kcal/day) based on protein, and vitamin and trace element supplement intake. The dietary regimen during the drainage and toning processes is based on a non-ketogenic low calorie diet (1,200 - 1,500 kcal/day) accompanied by protein products and vitamin and trace element supplements.
- Physical exercise. Toning exercises that increase in difficulty and intensity in each process.
- Application of a cosmetic cream. It is a cosmetic cream consisting of: red coralline algae, caffeine, red vine L-carnitine, and phosphatidylcholine.

According to the PnKCelulitis® program, the duration of the multidisciplinary treatment will vary between 61 days and 110 days, depending on the degree of cellulite assessed by the doctor who prescribes said treatment, according to the following scheme:

	Restructuring		Drainage	Toning
	1	2		
GRADE 1	7 days	14 days	20 days	20 days
GRADE 2	14 days	7 days	30 days	30 days
GRADE 3	20 days	20 days	40 days	30 days

Multidisciplinary treatment will be prescribed and controlled independently of this study by the prescribing physician as well as by the physical trainer and a team of dietitians from the Pronokal Group® Center. The doctor will be in charge to refer the patients to the Dermatology Service of the Santa Creu i Sant Pau Hospital to propose their participation.

9 STUDY MEASUREMENTS AND ENDPOINTS

9.1 Study endpoints

9.1.1 Primary endpoint

Differences in trabecular structure of subcutaneous tissue between the time prior to the multidisciplinary treatment and after the end of the treatment, assessed by skin ultrasound:

- Indented subcutaneous fascicles in the dermis (length: measured from the center of the base to the point of maximum indentation in the dermis)

9.1.2 Secondary endpoints

- Changes in other skin structural parameters between the time prior to the multidisciplinary treatment and after the end of said treatment, assessed by skin ultrasound:
 - Thickness of skin: thickness of dermis, thickness of epidermis and total thickness of the skin
 - Changes in the echogenicity of the dermis
 - Presence of dermal edema
 - Presence of nodules in the subcutaneous areolar tissue

- Changes in cellulite severity in the areas involved, between the time prior to the multidisciplinary treatment and after the end of treatment, assessed from photographic images, using the validated photonumeric scale of Hexel et al.⁷, which evaluates the following parameters:
 - Number of visible depressions (0 = none, 1 = 1 to 4; 2 = 5 to 9; 3 = 10 or more depressions)
 - Depth of depressions (0 = No depressions; 1 = superficial depressions, 2 = medium depth depressions, 3 = deep depressions)
 - Morphology of the epidermis (0 = flat, 1 = "orange skin" look; 2 = "cottage cheese" look; 3 = quilted look)
 - Grade of laxity or sagging (0 = absence of laxity/sagging; 1 = slight; 2 = moderate; 3 = severe)
 - Severity in accordance with Nürnberg and Muller scale(0 = zero grade; 1 = first grade; 2 = second grade; 3 = third grade)

The addition of the scores obtained will provide a final score that will allow the cellulite classification:

From 1 to 5 = mild cellulite

From 6 to 10 = moderate cellulite

From 11 to 15 = severe cellulite

9.2 Study plan and procedures

9.2.1 Recruitment of patients

Patients will be referred to the Dermatology Department of Hospital de la Santa Creu i Sant Pau, from the PronoKal Group® Center by the doctor who prescribes it regularly.

During the consultation, the dermatologist will explain the study to the patient and propose their participation. The patient will be provided with the information sheet and will be asked to sign the informed consent.

9.2.2 Follow-up of patients

Patient follow-up will be 10 ± 1 weeks to 18 ± 1 weeks, depending on duration of treatment depending on the degree of cellulite.

Only two controls will be performed: initial (prior to the multidisciplinary treatment) and final (after the end of the multidisciplinary treatment).

Initial visit

The inclusion and exclusion criteria will be assessed and the signed informed consent will be obtained. Demographic data (age) are recorded and the degree of cellulite is evaluated following the Nürnberg and Muller scale (0 = zero grade, 1 = first grade, 2 = second grade, 3 = third grade). The dermatologist will perform skin ultrasound and will take pictures.

Final visit

The dermatologist evaluations will be repeated: evaluation of the cellulite grade, accomplishment of skin ultrasound and photographic images.

9.2.3 Procedure for taking photographs

Photographs of the gluteal area (posterior) and hips (right and left), with the patient standing upright, 50 cm apart using a tripod, with an amplitude of focus from the iliac crest to the knee, always in the same place and the same lighting conditions.

Patients should wear disposable paper underwear, exposing the largest possible gluteal surface. Photographs will not include tattoos or other types of marks that identify the patient. Digital images will be saved and identified with the patient code.

The images will be assessed subsequently using the validated photonumeric scale, by two independent evaluators, blindly, that is, with a new coding that prevents them from identifying the patient or the visit to which it corresponds. The final result will be the average between both evaluations.

9.2.4 Procedure for the assessment of skin ultrasound

Ultrasound changes will be assessed at the end of the study. The ultrasound images will be saved with the patient and the visit code. At the end of the study, ultrasound changes will be assessed by two evaluators, independently and blindly. The final result will be the average between both evaluations.

The parameters to be controlled are:

- Dermis thickness
- Hypodermis thickness
- Total skin thickness
- Dermis echogenicity
- Assess presence of dermal edema
- Presence of nodules in areolar subcutaneous tissue

- Indented subcutaneous fascicles in the dermis (length: measured from the center of the base to the point of maximum indentation in dermis)
- Presence and quantity of perpendicular fibrous septa

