13 PRACTICAL CONSIDERATIONS

13.1 Workplan

The principal investigator will be in charge of including the patients referred to his office. Once the patient has read the Patient Information Sheet (Attachment 2) and confirmed their willingness to participate, the investigator will obtain the signature of the Informed Consent Form (Attachment 3) and must keep them with the rest of the documentation of every subject.

The doctor will record the data requested in the CRD and will perform the skin ultrasound and the taking of photographs. The ultrasound images will be saved digitally, identified by the patient and the visit code; and will be saved to be evaluated at the end of the study, blindly, by the principal investigator and by another evaluator separately. Similarly, the photographs will be saved in digital files identified with the patient and visit code. The latter will be recoded before evaluation by two independent evaluators to ensure the blindness of the patient and the visit in which the photographs were taken.

The investigator will not perform any clinical follow-up of the patients during the multidisciplinary medical treatment and will only visit the patients prior to and after the anti-cellulite program.

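### Blind reading is promised for the ultrasound images behind the primary endpoint, but the step that hides the visit is written only for the photographs

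*Combined protocol and SAP*

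**What the plan says.** Section 9.1.1 makes the before/after difference in the length of the indented subcutaneous fascicles, assessed by ultrasound, the primary endpoint. The photographs supply a secondary endpoint (Section 9.1.2).

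Blinding is clearly intended. Section 6.1 describes "A pilot, prospective, single blind, no controlled study with ultrasound evaluation of skin", and Section 9.2.4 says that "ultrasound changes will be assessed by two evaluators, independently and blindly".

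The handling of the two image types differs:

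- **Ultrasound.** Section 9.2.4: "The ultrasound images will be saved with the patient and the visit code". Section 13.1: "The ultrasound images will be saved digitally, identified by the patient and the visit code". Both sections then move straight to blind reading at the end of the study. Section 13.1 names the principal investigator as one of the two readers.
- **Photographs.** Section 9.2.3 explains what blind means: "blindly, that is, with a new coding that prevents them from identifying the patient or the visit to which it corresponds". Section 13.1, having described the ultrasound images and then the photographs, adds: "The latter will be recoded before evaluation by two independent evaluators to ensure the blindness of the patient and the visit".

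Section 6.4 covers both image types, but says of the evaluators only "who will not know the identity of the patients evaluated". Section 12.4 likewise deals with coding of identity and does not mention visit.

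**The concern.** Sections 6.2 and 6.3 state that randomization and control do not apply. The whole inference is therefore the comparison of the initial with the final visit, and in such a design the visit plays the part that treatment allocation plays in a controlled trial. Hiding a woman's identity while leaving the visit visible protects confidentiality, but it does not protect the comparison.

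A reader who knows which scan was taken after treatment may, without intending to, place the measuring points so that the fascicles look shorter. With no control arm to carry the same shift, it cannot be subtracted out. It appears as treatment effect.

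The only operational masking step in the plan protects a secondary endpoint. A team following the text literally could give both ultrasound readers files labelled by visit and still satisfy Section 6.4.

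**Working it through.** **1. The text, side by side**

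| | Ultrasound (primary endpoint) | Photographs (secondary endpoint) |
|---|---|---|
| Stored under patient and visit code | Yes (9.2.4, 13.1) | Yes (13.1) |
| Blind reading promised | Yes (6.4, 9.2.4, 13.1) | Yes (6.4, 9.2.3, 13.1) |
| Identity hidden from readers | Stated (6.4) | Stated (6.4, 9.2.3, 13.1) |
| Visit hidden from readers | Not stated | Stated (9.2.3, 13.1) |
| Recoding before reading | Not stated | Stated (9.2.3, 13.1) |

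The recoding sentence in Section 13.1 cannot be read as covering both types: it refers to the last-named item and ends by speaking of the visit at which the photographs were taken.

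**2. What a visit-linked reading shift would do**

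The plan gives no SD, reader error or bias, so there is no figure to reproduce. The shift below is an assumption shown over a range.

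Inputs: n = 30 (Section 7.4); significance level 0.05 (Section 10.2), taken as two-sided because sidedness is not stated; final value is the average of two readers (Section 9.2.4); true change zero. Section 10.2 names Student's t test without saying paired; a paired test is assumed first.

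Let b be the shift in the averaged reading, in SDs of the paired change. The standard error of the mean change is SD/√30 = 0.183 SD. The t statistic is then noncentral t with 29 df and noncentrality b√30, and the false-positive rate is P(|T| > 2.045). For b = 0.2, b√30 = 1.10 and the rate is 0.185.

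If only one reader is affected, averaging halves the shift, so b is replaced by b/2.

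| Shift (SD of paired change) | Rate if the averaged reading shifts by this much | Rate if one reader only shifts by this much |
|---|---|---|
| 0.1 | 8% | 6% |
| 0.2 | 19% | 8% |
| 0.3 | 36% | 12% |
| 0.4 | 56% | 19% |

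The nominal 5% doubles to 10% at b = 0.123 in the average, which is 2 × 0.123 = 0.246 in a single reader.

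**3. Sample size does not help**

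The noncentrality grows with √n. At b = 0.2 the rate is 19% with n = 30, 33% with n = 60 and 58% with n = 120. The bias in the mean change stays at 0.2 SD throughout.

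**4. If the t test is run unpaired**

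The rate then depends on the before/after correlation, which the plan does not give. Simulated trials of 30 pairs with b = 0.2 give about 10% at correlation 0.3, 5% at 0.5 and 0.9% at 0.7. At 0.5 without bias the rate is 0.7%. The unpaired test is too conservative on paired data, which hides the inflation; the bias in the estimated mean change is the same.

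**The case against.** The strongest reply is that the plan under-describes a procedure it intends. Blind reading of ultrasound is stated three times. Section 9.2.3 spells out that blind means hidden patient and visit, and the next section uses the same word for ultrasound. Storage under a visit code proves nothing, because the photographs are stored in the same way and are still to be read blind. This is fair as to intent: the text does not show that readers will see the visit. It does not supply the missing step. The authors wrote out visit masking twice for photographs and never for ultrasound, and the one masking statement that covers ultrasound readers names identity alone.

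A second reply is that this is an exploratory pilot whose endpoint is a length with a defined measuring rule, averaged over two readers. That makes it less open to expectation than a graded score. But averaging does nothing to a shift that both readers share, and the plan still tests at p < 0.05 (Section 10.2) and intends publication (Section 13.4).

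Third, the false-positive rates rest wholly on assumed shifts and on a paired test. That stands. They are illustrations, and under an unpaired test they can fall below 5%. The bias in the mean change does not depend on the choice of test.

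Fourth, recoding masks the reading only. Section 9.2.2 says "The dermatologist will perform skin ultrasound and will take pictures", and that person knows the visit. This also stands, as a limit on what recoding achieves; it is no reason to omit it.

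**Conclusion.** The concern holds. As written, visit masking of the primary endpoint is not secured, while the same masking is specified for a secondary endpoint. This must be fixed before the images are read. The reason is structural: visit is the only contrast in the study, the affected endpoint is primary, and neither more patients nor another test removes a visit-linked reading shift. That judgement does not depend on the illustrative rates, which run from 8% to 56% for assumed shifts of 0.1 to 0.4 SD in the averaged reading (paired t test, n = 30, two-sided 5%, no true change).

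A lesser ambiguity sits beside it. The principal investigator enrols the women and is one ultrasound reader (Section 13.1), the investigating physician holds the list linking codes to names (Section 12.4), and a dermatologist or doctor performs the scans (Sections 9.2.2 and 13.1). The available text does not say which of these are the same person. This is not a contradiction, but it makes explicit masking of the readers more important.

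**What to change.** Amend Sections 6.4, 9.2.4 and 13.1 as follows:

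- Extend the recoding of Section 9.2.3 to the ultrasound images. Before reading, remove patient code, visit code and date from the file and the image, and assign new random codes.
- Have both readers measure the images in random order, not as labelled before/after pairs.
- Name a key holder who is not a reader, and release the key only when both readers' measurements are final.
- State in Section 6.4 that readers are blind to visit as well as to identity.
- Clarify in Sections 6.4, 12.4 and 13.1 who holds the code list and whether a reader also performs the scans, and state that no reader uses the list or the originally coded files during reading.
- Acknowledge that image acquisition remains unmasked.

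Section 9.2.3 itself specifies only a new coding; date removal, random order and an independent key holder go beyond it and would suit the photographs as well.

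The cost is a small amount of file handling and one named key holder. No reader, visit or procedure is added. Because the images are read at the end of the study, the change can be made at any time before then. Once a reader has seen visit-labelled images, that reader cannot be reliably re-blinded.
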